4.2 POTENTIAL STUDY BENEFITS

Potential study benefits include improved access to early palliative care and end-of-life care outcomes in patients with advanced cancer.

4.3 STUDY DURATION

- 12 months (6 months enrollment; 6 months follow-up)
- We anticipate the semi-structured interviews take approximately three to four months. In a qualitative study, interviews are conducted until thematic saturation is achieved, and we anticipate this will be achieved with interviewing approximately 10 oncology clinicians in the intervention group and 10 palliative care clinicians.

4.4 TARGET POPULATION

Approximately 400 patients with advanced malignancies and up to 80 clinicians to assess response to behavioral nudges to refer to palliative care at up to 17 practices within Tennessee Oncology. The split will be into two arms: approximately 200 intervention, 200 control, and up to 40 clinicians in each arm. Clinicians will be clustered to a single practice for the intervention and analysis in order to avoid contamination of intervention effect into the usual care arm.

Our target population for the semi-structured interviews includes clinicians at Tennessee Oncology that were included either in the intervention group as oncology providers, and palliative care clinicians at Tennessee Oncology that saw patients referred through our intervention.

4.5 INCLUSIONS/EXCLUSIONS

Eligible clinicians will be medical oncology physicians and advance practice providers (APPs) practicing at Tennessee Oncology. Clinicians will be clustered to a single practice for the intervention and analysis in-order-to avoid contamination of intervention effect into the usual care arm. Patients will be excluded if they had a palliative care visit or had no medical oncology visit within the prior 12 months or are seen for a non-medical oncology encounter.

Eligible clinicians will receive notification about the trial via email and in-person presentations. High-risk patients for the intervention will be identified from weekly runs of the risk score algorithm (see **Exhibit 1**), in coordination with Tennessee Oncology Care Data Systems Manager.

Practicing medical oncology care clinicians that were in the intervention arm of our initial study and practicing palliative care clinicians at Tennessee Oncology are eligible for the semi-structured interviews. Medical oncology clinicians at Tennessee Oncology that were in control arm will be excluded.

Inclusion Criteria

- Clinicians:

- Medical oncology physicians and advance practice providers (APPs) practicing at Tennessee Oncology
- Patients:
 - Stage III and IV lung, and non-Colorectal GI cancers, defined using internal algorithms based on International Classification of Diseases (ICD) diagnosis codes, EHR entries, and manual screening
 - Received cancer treatment (chemotherapy or immunotherapy) in the past 6 months

Exclusion Criteria

- Patients:
 - Benign hematology, genetics, survivorship encounters; no prior EHR data;
 - Deceased or enrolled in hospice care
 - Had a palliative care visit within the prior three months
 - have not had a medical oncology visit within the prior 6 months or are seen for a non-medical oncology encounter

4.6 INTERVENTIONS

Clinicians of patients in both arms will receive education on the availability of early palliative care and performance reports. Clinicians in Arm 1 (intervention) will receive a EHR notification with option to opt-out (placed by the research coordinator, see **Exhibit 5**) for palliative care referral for any eligible high-risk patient, defined by a risk score ≥ 1 for Stage IV cancer patients and ≥ 2 for Stage III cancer patients. If the risk score is above 8, they will be scheduled within 2 weeks, and all other patients will be scheduled within 4 weeks. Clinician will have the option to opt-out for any patient by responding to the notification which will be sent to the research coordinator. If the clinician does not respond, the research coordinator will approach patient via telephone, explain the rationale for referral based on a predetermined script, and offer and schedule an outpatient or telemedicine palliative care consultation per patient preference. Follow-up visits will occur at the discretion of the palliative care clinician, usually monthly. Clinicians in both arms will receive monthly peer comparison emails that compare their palliative care referral rates against other clinicians.

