2.8 PALLIATIVE CARE UTILIZATION IMPROVEMENTS

Overcoming suboptimal clinician decision-making biases is key to increasing palliative care referrals. Principles from behavioral economics can inform “nudges” that change how clinicians receive information and make choices such as palliative care referral. Default, opt-out nudges that make the optimal choice the path of least resistance can mitigate clinicians’ status quo bias. Reframing clinicians’ prognoses via “triggered” identification of high-risk patients may combat optimism bias. Finally, peer comparisons use social comparisons to counter overconfidence bias in order to increase guideline-based practice. These strategies are associated with 10-25 absolute percentage-point increases in guideline-based practices such as statin prescribing and transition from brand to generic drugs. However, to our knowledge no published randomized trials have used behavioral strategies to improve palliative care utilization in advanced cancer.

Given rising demand for palliative care with constrained supply across the United States oncology care system, our contribution will be significant because it will leverage scalable automated predictive algorithms with a behaviorally informed intervention to increase palliative care utilization among high-risk patients with advanced cancer. This intervention is expected to create a feasible, adaptable, and acceptable process in a community oncology setting that increases palliative care utilization earlier in the advanced cancer disease trajectory.

3. **OBJECTIVES & OUTCOMES**

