4. STUDY DESIGN

4.1 RANDOMIZATION & RECRUITMENT

This 2-arm randomized trial (six-month enrollment; six-month follow-up) will enroll approximately 400 patients with advanced lung and gastrointestinal malignancies and 40 clinicians to assess response to behavioral nudges to refer to palliative care at up to 17 practices within Tennessee Oncology, a US community oncology network. All practices have access to palliative care and will be randomized to usual care vs. intervention. The outcome is completion of a palliative care visit within 3 months among high-risk patients.

We will randomize practices into two arms using permuted block randomization to balance practice size, baseline palliative care referral rate (see **Exhibit 1**). The Principal Investigator ([name]) and primary statistical analyst will be blinded to arm assignment.

This 2-arm randomized trial (six-month enrollment, six-month follow-up) is taking place at Tennessee Oncology. Tennessee Oncology, one of the nation’s largest, community-based cancer care specialists, is home to one of the leading clinical trial networks in the country.

Eligible clinicians will receive notification about the trial via email and in-person presentations. High-risk patients for the intervention will be identified from weekly runs of the risk score algorithm, in coordination with [name], Tennessee Oncology Care Data Systems Manager.

For the semi-structured interviews, the research team at Tennessee Oncology will create a list of potential clinicians. We will initially contact potential participants via email (see **Exhibit 6**), and if we do not get enough participation, coordinator and site investigator will do in-person recruitment with clinicians. For participants that agree to do the interview, clinical research coordinator will create a research ID for each participant that only key members of research team will have access to. Coordinator will subsequently create a de-identified dashboard to track mode of interview (in-person, virtual, telephone), length of interview, participant characteristics (gender, years in practice, palliative care v oncology, physician v nurse practitioner), and to store audio files, transcripts, and analysis documents. To ensure an adequate number of perspectives on the trial, we will use purposive

sampling to sample clinicians who performed at or above vs. below the median response to the intervention.

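### The monthly peer-comparison emails do not restrict the benchmark by arm, so default referrals in the intervention arm can raise the rate shown to control clinicians

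*Combined protocol and SAP*

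**What the plan says.** Section 4.6 of the combined protocol and SAP gives some components to both arms and one to the intervention arm alone.

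- Common to both arms: "Clinicians of patients in both arms will receive education on the availability of early palliative care and performance reports". In addition, "Clinicians in both arms will receive monthly peer comparison emails that compare their palliative care referral rates against other clinicians".
- Intervention arm only: "Clinicians in Arm 1 (intervention) will receive a EHR notification with option to opt-out (placed by the research coordinator"). If the clinician does not respond, the coordinator calls the patient and offers and schedules the consultation.

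Section 4.1 describes the comparator as usual care: "All practices have access to palliative care and will be randomized to usual care vs. intervention". The stated protection against spill-over, in sections 4.4 and 4.5, is to tie each clinician to a single practice so as to "avoid contamination of intervention effect into the usual care arm".

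Section 2.8 presents the email as an active device: "peer comparisons use social comparisons to counter overconfidence bias in order to increase guideline-based practice".

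The documents do not say which clinicians form the comparison pool, which patients form the denominator of the rate, what period it covers, or whether a referral placed by the coordinator counts as the clinician's own.

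**The concern.** The emailed measure is the referral rate, which the default referral acts on directly. If the pool spans both arms and default referrals are counted, the benchmark sent to control clinicians moves with the treatment given in the other arm. A control clinician would then be compared with a figure that is higher because other practices have the intervention.

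The single-practice rule stops a clinician from working under both arms. It does not govern a benchmark calculated across practices.

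If control clinicians respond by referring more, the control visit rate rises and the primary contrast shrinks. The pressure would be greatest where the intervention works best. Section 6 makes no allowance for this, and analysis could not readily undo it, because every control clinician receives the email and no unexposed control group remains. Section 8.3 already accepts that control behaviour is sensitive: it argues that seeking consent from the control group could by itself change what they do.

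**Working it through.** **Inputs from the documents**

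- Section 6.5: control rate 26.9%, difference 15 points (so 41.9% with the intervention), two-sided alpha 0.05, dropout 10%, 180 patients per arm, stated power 80%, and 8–10% of eligible patients flagged as high-risk.
- Section 4.4: about 200 patients per arm, and "up to 40 clinicians in each arm".

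**Assumptions not in the documents**

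- The benchmark pools two equal arms, uses concurrent data and counts default referrals.
- Referral rates differ between arms by the same 15 points planned for visits.
- Control visits rise by 1, 3 or 5 points in response.

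**Step 1: reproduce the plan's power.** For two independent proportions with pooled variance under the null:

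power = Φ{ [d√n − 1.96√(2p̄(1−p̄))] / √(p₀(1−p₀) + p₁(1−p₁)) }

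Here p₀ = 0.269, p₁ = 0.419, d = 0.15 and p̄ = 0.344.

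- n = 180 × 0.9 = 162: (0.15 × 12.728 − 1.96 × 0.6718) / 0.6634 = 0.893, so power is 81.4%.
- n = 180: (0.15 × 13.416 − 1.96 × 0.6718) / 0.6634 = 1.049, so power is 85.3%. This size is reached with no dropout from 180, or with 200 × 0.9 from the section 4.4 target.
- In reverse, 80% power needs 157 evaluable per arm, and 157 / 0.9 ≈ 175, close to the planned 180.

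The stated 80% therefore reproduces, with patients treated as independent and the control rate fixed at 26.9%.

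**Step 2: how far a pooled benchmark would move.**

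- Rate calculated in high-risk patients only: (26.9 + 41.9) / 2 = 34.4%, which is 34.4 − 26.9 = 7.5 points above the control mean.
- Rate calculated in all eligible patients, with rates in the others unchanged: the intervention-arm rate moves by 15 × 0.08 = 1.2 to 15 × 0.10 = 1.5 points. The pooled benchmark moves by half of that, 0.6 to 0.75 points.

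The unstated denominator alone changes the shift by a factor of 10 or more.

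**Step 3: what a given control response would cost.** The intervention rate stays at 41.9%, and the Step 1 formula is used with p₀ raised.

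| Assumed rise in control visits | Remaining contrast | Power, 162 per arm | Power, 180 per arm | Evaluable per arm for 80% |
|---|---|---|---|---|
| 0 points | 15 points | 81.4% | 85.3% | 157 |
| 1 point | 14 points | 75.5% | 79.8% | 181 |
| 3 points | 12 points | 61.6% | 66.1% | 250 |
| 5 points | 10 points | 46.2% | 50.2% | 365 |

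These powers ignore clustering by practice, as the plan's own figure does. They show relative loss and do not predict the trial's actual power. Nothing in the documents links the benchmark shift in Step 2 to a particular row of the table.

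**The case against.** The best defence is that the plan leaves the email undefined, and that the harm needs three things together: a pool that crosses arms, concurrent data, and default referrals counted as the clinician's. The sponsor may already intend a same-arm report. This limits how firmly the harm can be asserted. It does not answer the point, because the only rule stated is a comparison with other clinicians and no section narrows it.

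Other parts of the defence stand:

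- An upward response among controls pulls the result toward no difference, so it cannot manufacture a benefit.
- Exposure is limited. The emails are monthly, and control patients enrolled early pass much of their 3-month window before many reports have gone out.
- Awareness of the trial does not come from the email alone. Eligible clinicians are already told of it by email and in presentations (4.1, 4.5).

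A reader might also infer more than the documents support:

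- *That controls are ranked, or told that they lag.* The text says only that rates are compared.
- *That sending emails to both arms is itself contamination.* It is a common co-intervention and does not by itself bias the contrast. The issue is the content of the benchmark.
- *That the email defeats the clustering of clinicians, or builds interference into the design.* The single-practice rule still does its own job. It simply does not reach the benchmark.
- *That the 10–25 point changes in section 2.8 indicate the size of the leak.* Those figures describe several behavioural strategies together, in practices such as statin prescribing. Here both arms receive the email, and what matters is the extra response to a higher benchmark, on which the documents are silent.

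**Conclusion.** The point holds as a contamination path left open by the wording of section 4.6. On the plain reading, the benchmark sent to control clinicians can rise because of default referrals in the other arm, and the single-practice rule does not prevent it. Any resulting increase in control visits biases the primary contrast toward no difference.

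The documents do not support a claim that the leak is large or certain. Under the stated assumptions the benchmark shift runs from about 0.6 to 7.5 points, depending on the denominator, and the clinicians' response to it is unknown. The power losses are a sensitivity range for assumed responses. They do show that the plan has little slack: a 1-point rise in control visits takes power just below 80% even at 180 evaluable per arm. This should be fixed, since prevention is cheap and correction in analysis is not available. The evidence does not make it a fatal flaw.

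**What to change.** In section 4.6, replace the open comparison with other clinicians by a comparison with clinicians in the same arm. A fixed pre-trial network benchmark is an acceptable alternative. State the denominator of the emailed rate, and use the same template in both arms. Either benchmark keeps default referrals out of the figure shown to controls.

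It would be tempting to count only clinician-initiated referrals as well. That is not advised. With a same-arm or fixed benchmark it adds nothing for controls. In the intervention arm, default referrals can replace referrals the clinician would have made, so the emailed rate could fall because of treatment. Against a fixed benchmark, those clinicians would then appear to fall short while their patients are being referred.

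The cost is one or two sentences in section 4.6 and a filter in the monthly report. A same-arm benchmark rests on fewer clinicians: up to 40 per arm by section 4.4, or about 20 if the 40 clinicians in section 4.1 are the total and split evenly. A fixed benchmark ages over the six-month enrolment. Both drawbacks are minor.

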4.7 INNOVATIONS

Prior retrospective studies have analyzed the effect of educational or trigger-based strategies on palliative care utilization. However, three factors limit generalizability: (1) lack of a prospective, randomized design; (2) academic study settings with different patient populations and palliative care capacity than most US oncology practices; and (3) referral triggers that require substantial clinician cognitive effort. Our approach of a pragmatic randomized clinical trial is unique. Furthermore, our behavioral intervention, using default referrals based on an automated EHR algorithm, tests a scalable approach to increasing palliative care utilization. Finally, we will use post-intervention semi-structured interviews to refine this approach prior to submitting an R01 application for a multi-institutional randomized clinical trial that includes algorithm-based behavioral strategies to increase palliative care referral in community oncology.

4.8 COHORT MALIGNANCIES

Stage III and IV lung and non-colorectal Gastrointestinal (GI) cancers, defined using internal algorithms based on administrative codes, EHR entries, and treatment regimens. These malignancies represent 43% of solid tumor deaths in the US, have positive prospective evidence for early outpatient palliative care, and have been used in prior Tennessee Oncology palliative care pilots.

4.9 ACCRUAL

Patients will accrue to the trial as their clinic or clinician is enrolled. **Included** Tennessee Oncology practices will be randomly assigned to usual care or intervention groups. When enrollment starts, clinicians in the intervention clinics will receive the EHR nudge for palliative care referral for each eligible patient and based on the clinician response (opt-out or default), the research coordinator will call and offer palliative care consultation visit to the patient.

For the semi-structured interviews, participants will be initially recruited via internal practice email (See **Exhibit 6**) from the clinical research coordinator. If we don't receive enough interest, we will then recruit by visiting the clinicians in-person in their clinics. In-person recruitment will be done by site investigator and/or clinical research coordinator at Tennessee Oncology.

Approximately 20 eligible clinician participants from the intervention group will be interviewed (1) in-person, (2) virtually, or (3) via telephone. To ensure an adequate number of perspectives on the trial, we will use purposive sampling to sample clinicians who performed at or above vs. below the median response to the intervention. The clinical research coordinator will email and schedule the interviews through outlook. A confirmation email will be sent to the clinician 24 hours before the interview unless the interview will occur less than 24 hours after scheduling. Two pilot interviews will be conducted and used in analysis (pending major edits are not required).

4.10 QUALITATIVE PROCEDURES

1. Interviews will be conducted in-person or virtually at a time and location that is convenient for the participant. Typically, this would be in their home clinic within their private office space. If needed, there is office space available in our practice administrative suite in Nashville, TN. If it is difficult to schedule an in-person interview, or if the interviewer is the Penn CRC, we will offer a virtual (zoom or skype) interview or telephone interview.
2. There will be two CRCs conducting interviews for this study. One of the CRCs is based at Tennessee Oncology and one is based at Penn. Both will be trained by the research team on conducting semi-structured interviews.
3. All interview supplies will be readied before the interview begins. The following items are needed: recorder and charger, laptop and charger, interview guide.
4. At time of interview, clinical research coordinator (interviewer) will follow the listed procedures in order:
 - a. A final confirmation will be made that the clinician can talk at that time
 - b. The interviewer will confirm the email or address to which compensation should be sent after the interview.
 - c. Interviewer will obtain verbal consent using the consent language included in the appendix.

Confidential

- d. Interviewer will begin recording on audio recording device or Zoom. Interviewer will state clinician ID number and date of the interview.
 - e. Interviewer will conduct semi-structured interview based on a prepared interview guide with open-ended questions either in-person, over Zoom, or on the telephone.
 - f. To wrap up interview, the interviewer will ask if the clinicians has any final thoughts or questions. Once these are addressed, interviewer will state that recording will stop, and the interviewer will stop the audio recorder.
 - g. At the end of the interview, the interviewer will debrief the participant. This is not a structured process, but rather time to answer any questions the participant has about the study. We don't anticipate significant enough emotional distress in clinical providers to warrant support resources.
5. Immediately following the end of the call, the interviewer will save the audio recording on a password-protected laptop, upload to Monday.com study dashboard, and memo the interview by writing down an overall summary of the interview and if there is anything else that was noteworthy. This document will be saved for future use as needed in Monday.com.
 6. The interviewer will also send a brief thank you note and incentive via email.

Post-Interviews

1. As the interviews are being completed, audio recordings will be collected and sent for transcription by a third-party transcription company. When files are sent to the external company, the staff member will note to the transcribers to remove any individual names of people (e.g., clinicians, health system leaders, staff, patients), sites, etc. that have been used in transcript if any are mentioned during recording.
2. After transcription has been completed, the coding and analysis process will begin.

Coding Interviews

1. Interview coding will require a minimum two individuals (this can include the interviewing research staff member)
2. Both coders will carefully read each interview and then meet to discuss common themes
3. Once coders have discussed common themes, a list of coding nodes will be created for use in Dedoose qualitative software.
4. One coder will import the transcripts and insert the node list in a single file. Both coders will use this same origin file as they code.
5. The coders will meet every 2-3 interviews that they code to discuss their coding and to ensure that there are few to no discrepancies between coding styles.
6. The two coders will each code all transcripts.
7. The codebook will be edited on an ongoing basis as needed, as determined by the emergence of new themes.
8. Following the completion of successful coding, Dedoose can be used to pull different qualitative data points as needed for analysis.
9. Coders will develop theme sheets based on those excerpts identified in coding as relevant to each theme
10. The team will review theme sheets and discuss the message of each theme.

11. The team will come to consensus on quotes that are exemplary of each theme.

